3.3 PARTICIPANTS

Participants will be junior doctors (of any specialty, pre-certificate of completion of training) and junior nurses (of any specialty, band 5 to 6), currently working and training within the NHS or a private healthcare hospital in England. All participants must be able to communicate and write in English. They must be willing to engage with a mobile learning resource as an additional task to their clinical role, ensuring their learning does not take time out of their clinical commitments. Potential participants will be excluded if they are undergraduates, completed their training or retired.

There will be no coercion or pressure to participate. There will be no monetary reward for participation. Participants may use the SPE as a work-based assessment to be completed by the CI upon request.

3.4 SAMPLE SELECTION, PERMISSION & INVITATION

Recruitment of potential participants will utilise a number of methods. As the sample population will be those currently training and working within the hospital setting, the CI has the opportunity to present the study to doctors and nurses in training in their grand-rounds, trainee teaching sessions and department meetings. Having established contacts with the medical and nursing postgraduate training leads, the CI aims to disseminate e-mail invitations (see appendix 1A) to potential participants through the training leads. Once potential participants have been identified, a snowball approach will be used to identify further potential participants through peer word-of-mouth and recommendation. Finally, e-mail invitations will be disseminated through the CI and co-investigator's personal contacts, and through contacts of those working within the Department of Surgery and Cancer. Potential participants will be given up to two weeks to decide if they want to participate, with a reminder sent after one week (appendix 1B).

Potential participants will be sent a participant information sheet (PIS) (appendix 2) attached to the invitation e-mail. The number of potential participants who have been e-mailed will be tallied by the CI on an Excel spreadsheet to compare the number of those who have been approached as potential participants to those who become study participants. Each potential participant will be referenced by a participant ID number for confidentiality purposes.

3.4 CONSENT

Respondents to the invitation will be given the opportunity to read a paper-copy of the PIS and provide written consent (appendix 3) to join the study. Consent will be gained by the CI at a time that is convenient to the potential participant. Participants will be randomised once consent is signed and the baseline questionnaire is completed.

3.5 MEASURES

Questionnaires

Once consent is gained, the participants will complete a baseline (pre-intervention) questionnaire (appendix 4) reporting their demographics, previous exposure to breaking bad news training and their engagement with mobile learning resources. The questionnaires will be printed and available for completion following consent. If participants would rather have more time to complete the questionnaire, an electronic version will be sent via e-mail for them to complete and return within two weeks.

The post-intervention questionnaire (appendix 5) will be offered at the time of the second SPE (four to six weeks following randomisation). If any participants wish to not attend the SPE, the post-intervention questionnaire will still be offered to them. Participants will be given two weeks to complete and return the questionnaire.

The questionnaires utilise a five-point Likert scale (37,38) ranking of the user's confidence and agreeability with statements. Some statements have a white space to write comments. The questionnaires are novel to this study and were developed using principles of Kirkpatrick's Model of Learning Evaluation (39), the Theory of Planned Behaviour (40) and the Technology Acceptance Model (41), whilst also drawing on the most important curricula competencies derived from the content analysis of a sample of medical and nursing curricula followed by an expert consensus (unpublished work by CI).

Simulated patient encounters

SPEs allow assessments of skills in a safe and controlled environment, without impacting patient care (42). Participants will be asked to complete two SPEs – the first at baseline, and the second four to six weeks post-intervention. The CI will send dates for the candidates to choose the best time for the SPE. The participants will have to ensure the time taken for the assessments are outside their clinical commitments or they have adequate clinical cover if they are participating during work hours. Those working within the same department will be encouraged to participate on the same day to avoid discussion within the group of participants who have and have not completed the SPE. The SPEs will be arranged within the hospital premises where the participants work or within the premises of the Academic Surgical Unit at Imperial College London.

Prior to the start of the SPE, the participant will be given a participant task sheet to read, which summarises the task (appendix 6A and an example in appendix 6B). They will be reminded that their personal performance scores will remain confidential (not distributed beyond the CI and his co-investigators). They will be offered the opportunity to have the consultation documented as a work-based assessment for their portfolio.

The participant will be given 15 minutes to conduct a consultation with a SP where they have to break bad news. The SP will be role-played by a professional actor/patient known to Clinical Skills team within the Department of Surgery and Cancer, from a bank of professional actors/patients who have experience in communication skills training and have previously been trained to participate in SPEs. The actor/patient will be compensated for their time according to their agreement with the department. A short introduction to their character and how they may respond to questions and ques will be provided (appendix 7A and an example in appendix 7B). Task and character sheets are adapted from templates provided by MockOSCE (43). Separate scenarios will be used at baseline and post-intervention. The previously validated Breaking bad news Assessment Schedule (BAS) (36) will be used as the mark sheet (appendix 8) to quantify participant interaction with the SP. The BAS has been shown to have high internal consistency (Cronbach's alpha score of 0.93) and the interrater reliability was within the moderate to good range (weighted kappa values 0.4510, 0.6817 and 0.6114) (36). The mark-sheet will be completed by the SP and the CI at the time of the SPE. The encounter will be video-recorded so that it can be viewed by the independent assessor at a later date to complete the mark sheet. Therefore, three separate assessor scores will be used when calculating the overall performance score of each participant.

Following the completion of the SPE, the participant will be reminded not to discuss the scenario with other members of their department who have not yet completed the consultation. Following the completion of the second SPE and the post-intervention questionnaire, the participants will have no further commitments to the study.

Semi-structured interviews

To greater understand the participant's ability to break bad news following their use of the learning resource, they will be asked to participate in semi-structured interviews soon after the completion of the post-intervention questionnaire. During the interview, they will be asked about their ability to break bad news, how the learning may have impacted their clinical practice, their perception of their performance in the SPEs, and how they interacted with the learning resource in practice.

Participants will be read a short introduction prior to the start of the interview (see appendix 9). They will be reminded that what they disclose in their interview will remain anonymous. They will be informed that the interview will be audio recorded, transcribed and anonymised. A list of topics will guide the semi-structured interviews (see appendix 9). The interviews are expected to last 15- 30 minutes. An audio recording will be made of the interview and the researcher may take field notes documenting non-verbal responses and any reflections to be used to adapt the topic guide or study direction.

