3. STUDY DESIGN

3.1 METHODOLOGY & DESIGN

The study objective will be investigated through a pre-post mixed methods pilot study (see figure 1).

Potential participants will be sent invitation e-mails (appendix 1A and 1B). Once potential participants have read the participant information sheet (PIS) (appendix 2) and given consent (appendix 3), they will be asked to complete a baseline questionnaire (appendix 4) to understand their demographics, their previous exposure to breaking bad news (through formal or informal training) and their engagement with digital resources.

Following consent, participants will be asked to complete a baseline simulated patient encounter (SPE) with a simulated patient (SP) (role-played by a professional actor/patient) to assess their baseline ability to break bad news. Participants will be given a task sheet (appendix 6A) with a brief history of the SP and what news they need to deliver. The details and history of the SP will be documented on a character sheet (appendix 7A) for the professional actor/patient to refer to. The SPE will last 15 minutes and it will be video-recorded. The SPEs will be evaluated against a validated mark sheet (36) (appendix 8) completed by the SP, the CI (immediately following the SPE) and an independent assessor (by watching the video footage).

Following the pre-intervention SPE, access to the mobile learning resource will be granted. The mobile learning resource is the freely available VitalTips mobile application, provided by VitalTalk. The participants will be expected to spend at least three hours using the VitalTips app, without this time impacting on their clinical and academic commitments. As the in-application metrics will not be available to the researchers, participants will be asked to self-report their engagement with the resource in the post-intervention questionnaire (appendix 5).

Four to six weeks later, all participants will be asked to complete a second videoed SPE, which will be marked as described above. The participants will also be asked to complete a post-intervention questionnaire to gauge the impact on their clinical practice and their engagement with the mobile resources. Each participant will act as their own control when comparing the baseline and post-intervention SPE scores and questionnaire responses.

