7. STATISTICS & DATA ANALYSIS

7.1 SAMPLE SIZE

Due to the exploratory nature of this educational pilot study, the sample size will be relatively small, especially as all participants will be given the intervention and there are no comparator groups. Considering that there are two professional groups involved (doctors and nurses) a sample of ten participants from each (20 in total) should be sufficient to answer the research question and allow for thematic analysis of the post-intervention interview transcripts.

Schildmann et al. and similar studies either did not formally report on or had low attrition rates as their interventions were part of the participant's training (44). This makes it difficult to estimate the level of attrition in our study, especially as the intervention is not mandatory for training. However, it is estimated that attrition levels will be low as evidenced by similar studies.

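### No rule is stated for assigning the two simulated cases; if everyone takes the same case at each time point, case difficulty cannot be separated from the pre-post BAS change

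*Combined protocol and SAP*

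**What the plan says.** Section 3.5 (Simulated patient encounters) plans two encounters, the second four to six weeks after the intervention, and says: "Separate scenarios will be used at baseline and post-intervention". It does not say how many cases exist or who takes which. Appendices 6A and 7A are blank templates; 6B and 7B give one worked example.

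Section 3.1 sets the comparison: "Each participant will act as their own control when comparing the baseline and post-intervention SPE scores and questionnaire responses". Section 7.1 confirms that "all participants will be given the intervention and there are no comparator groups". Section 7.2 specifies a paired t-test on the BAS scores at p < 0.05, with no covariate.

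Two safeguards protect the cases from being passed on. Section 3.5 says: "Those working within the same department will be encouraged to participate on the same day". It also says that, after an encounter, "the participant will be reminded not to discuss the scenario with other members of their department who have not yet completed the consultation".

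The section 3.4 on consent says: "Participants will be randomised once consent is signed and the baseline questionnaire is completed". Nothing in the protocol links this to case order.

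**The concern.** Using each participant as their own control removes stable differences between people. It does not remove a shift shared by everyone, and a change of case between the two encounters is such a shift if all participants meet the cases in the same order. An easier second case could raise scores without any learning; a harder one could hide a real gain or turn it into an apparent decline.

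The BAS is the study's only assessor-rated measure of its objective. The protocol states a directional hypothesis (section 1.3), calls 20 participants sufficient to answer the research question (section 7.1) and applies a significance threshold. The interpretation of that test therefore depends on an assignment rule that the protocol does not give.

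**Working it through.** **Is a common order a fair reading?** Three places point to it without settling it. The non-discussion reminder in section 3.5 speaks of one scenario shared among colleagues. The Appendix 6B task sheet serves both doctors and nurses. The Appendix 9 topic guide asks about two case scenarios.

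**Is the score case-dependent?** In part. Appendix 8 item 16 is scored by how many of the concerns on that case's character sheet were aired. Most of the 23 items rate general process, such as greeting, pausing, inviting questions and body language.

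**Can the scores separate case from time?** Take a model with 20 participant effects, one time effect and one scenario effect (22 parameters). With one common order, the time and scenario columns are identical and the design has rank 21. With both orders in use the rank is 22. Adding a scenario term to the planned analysis would not help under a common order, because it could not be estimated.

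**How sensitive is the planned test?** The protocol gives no effect size, SD or power, so there is no figure of its own to reproduce. Inputs:
- n = 20 (section 7.1), and n = 15 as the lower end of the Study Summary range;
- alpha 0.05 (section 7.2), taken as two-sided;
- d = true change and c = shift due to the case, both in SDs of the paired difference. The values of c are assumptions.

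The t statistic is noncentral t with n − 1 df and noncentrality (d + c)√n. Critical values are 2.093 (n = 20) and 2.145 (n = 15).

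With d = 0:

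| c | n = 20: noncentrality | n = 20: p<0.05 | n = 15: noncentrality | n = 15: p<0.05 |
|---|---|---|---|---|
| 0.25 | 1.118 | 18.6% | 0.968 | 14.7% |
| 0.50 | 2.236 | 56.5% | 1.936 | 43.8% |

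In the other direction, a true gain with 80% power (0.66 SD at n = 20, 0.778 SD at n = 15) is detected as an improvement in about 41% (n = 20) or 48% (n = 15) if the second case is harder by 0.25 SD, and in 10% or 17% if harder by 0.50 SD. These figures apply to any shift common to all participants. They do not show that case difficulty differs here.

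**What do both orders achieve?** Let c be the amount by which B is easier than A. The paired difference has mean d + c in the A-then-B sequence and d − c in B-then-A. Regressing it on sequence coded +0.5/−0.5 makes the intercept the mean of the two sequence means: [(d + c) + (d − c)]/2 = d. In simulation at 10/10 with no true change and c = 0.5, this test rejected in about 5% of runs. A plain paired t-test on the same data was unbiased but conservative, at 2.9%.

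**Precision.** The ratio of CI half-widths, new to planned, is [t(n−2) × 0.5√(1/n₁ + 1/n₂)] ÷ [t(n−1)/√n].
- 10/10: (2.101/2.093) × 1.000 = 1.004
- 8/7: (2.160/2.145) × 1.002 = 1.010 (unrounded inputs)
- 12/8: (2.101/2.093) × 1.021 = 1.024
- 14/6: (2.101/2.093) × 1.091 = 1.095

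These ratios ignore any clustering by department.

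**The case against.** The strongest reply is that the fault is conditional. The protocol does not say that everyone takes the same case at each time point, and Figure 1 and the actual case sheets are not available to read, so an operational order plan cannot be excluded. That stands. What is established is that no assignment rule, equating step or scenario term is stated.

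A second reply is that this is a small exploratory pilot, with questionnaires and interviews alongside the BAS, and that different cases avoid recall of the first. Both points are fair. They limit the weight of the matter, but do not answer it while a p-value is attached to the BAS change.

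A third is that using both orders weakens an existing safeguard. Both cases then circulate from the first encounters, and recruitment makes contact likely, since "a snowball approach will be used to identify further potential participants through peer word-of-mouth and recommendation". Leakage would tend to raise second-encounter scores in both sequences, and a sequence term cannot remove it. This is a good argument against mixing orders within a department. It is weaker against one order per department, which keeps the second case new within each department. Leakage is also possible under a fixed order: same-day testing is only encouraged, and recruitment runs to the end of June.

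Three stronger readings are tempting and unsupported. A reader might take the randomisation sentence as covering case order, but nothing says so. With the Figure 1 caption and the intervention-group wording in Appendix 5, it reads more like a remnant of a two-arm design. A reader might infer that live markers are known to be aware of the time point. Section 3.5 says only: "The mark-sheet will be completed by the SP and the CI at the time of the SPE". Awareness is a reasonable inference for the CI, who arranges the encounters, but is not stated for the SP. A reader might also take the percentages above as an estimate of bias in this study; they rest on assumed shifts.

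**Conclusion.** The point holds in conditional form and is worth fixing; confidence is moderate. If one case order is common to all participants, the paired comparison estimates change over time plus the difference in case difficulty, and no later analysis of the collected scores can divide them. If cases vary between participants, the assignment is still unstated and unmodelled. Neither the size nor the direction of any bias can be known from the documents. The case-dependence of item 16 makes some shift plausible, while the general-process items may limit it. Removing the scenario component would not by itself make the BAS change attributable to the app.

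**What to change.** Before the first encounter, replace the scenario sentence in section 3.5 with:

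*Two scenarios (A and B) will be used. About half of participants will take A at baseline and B post-intervention, and the rest the reverse, with participants from the same department given the same order and the two orders kept as balanced as possible overall and by profession.*

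Then:
- Note department at allocation. It is not among the fields listed in section 3.6, which also says that the hospital is not recorded.
- In section 7.2, regress the paired difference on sequence coded +0.5/−0.5 and test the intercept. Do not centre sequence on its sample mean: with unequal groups that leaves (n₁ − n₂)/n of the scenario shift in the estimate, or 1/15 = 6.7% at 8/7.
- Extend the non-discussion reminder until all second encounters are complete.
- State that this removes only the scenario component. Practice from the first encounter, calendar time, other training and possible assessor knowledge of the time point remain limitations.

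The cases, actors and sessions are unchanged. The cost is one degree of freedom (CI about 0.4% wider at 10/10, 1.0% at 8/7), rising to 2.4% at 12/8 and 9.5% at 14/6 before any department clustering, plus possible leakage between departments. Section 8.1 says HRA approval is already held, so an amendment step may be needed; the documents do not describe its cost.

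If encounters have already run in one fixed order, report case difficulty as a confounder and do not attribute the BAS change to the app.

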3.2 STUDY SETTING

Participants will be recruited from hospitals within two NHS trusts - Imperial College Healthcare NHS Trust and Barts Health NHS Trust, and one private health care site - Bupa Cromwell Hospital. The intention is to recruit those working across a range of specialities, where staff frequently break bad news (e.g. oncology).

The study is intended to commence in January 2019 (dependant on HRA ethical approval) with final recruitment to be at the end of June 2019, to complete the study by August 2019.

Figure 1: Outline of quasi-randomised controlled trial

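### The instruction not to reveal the simulated case stops at the participant's own department, recruitment does not, and no form asks whether the case was already known

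*Combined protocol and SAP*

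**What the plan says.** Section 3.5 (simulated patient encounters) contains two safeguards against participants learning the case from each other.

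- Scheduling: "Those working within the same department will be encouraged to participate on the same day to avoid discussion within the group of participants". The aim is to keep people already assessed from talking to people still waiting. This is encouraged, not required, and participants pick their own slot: "The CI will send dates for the candidates to choose the best time for the SPE".
- Reminder: once the encounter is over, "the participant will be reminded not to discuss the scenario with other members of their department who have not yet completed the consultation".

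The same section uses different scenarios before and after the intervention. It does not say how many versions exist at each time point.

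Recruitment has several routes (section 3.4). The chief investigator can "present the study to doctors and nurses in training in their grand-rounds, trainee teaching sessions and department meetings", and training leads forward e-mails. Then "a snowball approach will be used to identify further potential participants through peer word-of-mouth and recommendation", and lastly "e-mail invitations will be disseminated through the CI and co-investigator's personal contacts". Section 3.2 adds "The intention is to recruit those working across a range of specialities", at two NHS trusts and one private hospital, from January to the end of June 2019.

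**The concern.** By including these safeguards, the plan accepts that knowing the case would spoil the assessment. The question is whether they reach everyone who could pass a case on or receive one. As worded, a participant is not asked to keep the case from a colleague in another department, at another hospital, or met at a teaching session, even if that colleague is about to take part.

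The main comparison is each participant's own change in BAS score, with no comparator group (section 7.1). Knowing the second case could raise the post-intervention score without any learning. Knowing the first could raise the baseline and hide learning. No control arm would share the bias and cancel it, and no dedicated question would record who was affected.

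**Working it through.** The plan gives no figure on this point, so the check is a comparison of the text followed by an illustration of size.

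**1. Scope of the safeguards against scope of recruitment**

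| Element | Reach |
|---|---|
| Reminder (3.5) | own department only |
| Same-day scheduling (3.5) | own department only, encouraged |
| Separate scenarios (3.5) | stop one person meeting the same case twice; do not stop one person telling another |
| Recruitment (3.2, 3.4) | several specialities, three organisations, teaching sessions, peers, personal contacts |

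The uncovered group is participants who know each other but work in different departments.

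**2. Would it be recorded?** The post-intervention questionnaire (Appendix 5) asks about other training and other mobile resources. The topic guide (Appendix 9) has an open question about the two scenarios. The mark sheet (Appendix 8) has a free notes field. None asks about prior knowledge of the case. Hospital is deliberately not recorded and department is not among the listed data (3.6), so the data set cannot show who might have shared a case. Section 7.2 plans no check.

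**3. Can it move the score?** The BAS has 23 items scored 1 to 5. Item 16 scores the character-sheet concerns that were aired, so foreknowledge can add at most 5 - 1 = 4 points there. Items 10, 15, 17 and 18 (concerns, accuracy, key areas, psychosocial issues) could plausibly benefit too. If items are summed, one extra point on each of the five gives 5 points and two extra gives 10. These gains are assumptions.

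**4. Size.** If k of n participants know the second case and each gains g, the mean change shifts by k × g / n. Measure g in SDs of the paired difference, so the standard error is 1/√n = 1/√20 = 0.224. Assume no true effect, foreknowledge of the second case only, and the planned two-sided paired t-test at 0.05. The last column comes from 200,000 simulated trials per row (n = 20).

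| k | g | shift kg/n | shift ÷ 0.224 | P(p < 0.05) |
|---|---|---|---|---|
| 2 | 0.5 | 0.050 | 0.22 | 5.3% |
| 2 | 1.0 | 0.100 | 0.45 | 6.0% |
| 5 | 0.5 | 0.125 | 0.56 | 7.5% |
| 5 | 1.0 | 0.250 | 1.12 | 14.2% |
| 10 | 0.5 | 0.250 | 1.12 | 16.9% |
| 10 | 1.0 | 0.500 | 2.24 | 46.8% |

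With n = 15 (the low end in the study summary) and k = 4, the shift is 4 × 0.5/15 = 0.133 to 4 × 1.0/15 = 0.267, and the rate is 7.0% to 12.0%. For scale, 80% power needs a standardised paired effect of 0.66 at n = 20 and 0.78 at n = 15.

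In points, with an assumed SD of change of 8 to 15, the standard error is 8/√20 = 1.79 to 15/√20 = 3.35. Two people gaining 5 points shift the mean by 2 × 5/20 = 0.5; four gaining 10 shift it by 4 × 10/20 = 2.0. The top of the g range is generous: at SD 15, g = 1.0 means 15 of the 5 × 4 = 20 extra points those five items could yield.

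**The case against.** The case on the other side is substantial.

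- **Reuse is not stated.** The harm needs a later participant to meet the same case. The appendices give blank templates and one example. Reuse is an inference, though a fair one: the two department-level safeguards would serve no purpose if every participant had a new case.
- **Referral is not disclosure.** A reader might infer that recruitment depends mainly on participants passing the study to peers, and that those peers are the likeliest to hear the case. Section 3.4 does not support this. Snowballing is one route of several and starts once potential participants are identified, so a referral may precede the referrer's first encounter. Referred peers may also share a department and so be covered.
- **The gain may be small.** Everyone reads a task sheet with the history and the news before starting, so foreknowledge adds mainly the patient's concerns and preparation time. Many BAS items score conduct such as greeting, pausing and body language.
- **Leakage might still surface.** A reader might conclude that it could never be detected. That goes too far: a participant could mention it at interview, or an assessor could note it. What is missing is a dedicated question.
- **Other documents may cover it.** The information sheet and consent form are not in the available text and may ask for wider confidentiality.

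These points limit the size and certainty of the problem. They do not change the fact that both safeguards, as written, are narrower than recruitment.

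**Conclusion.** The point holds as a minor gap. The plan names the threat and then guards against it only within departments, while recruiting across departments and organisations. The conclusion rests on scenarios being reused at a time point and on the missing participant documents not already containing a wider request.

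The documents do not show that leakage will occur, and its net direction is unknown because first-case and second-case knowledge act in opposite ways. The size depends on assumed inputs. With 2 of 20 affected at the second encounter the false-positive rate barely moves; with 5 it reaches 7.5-14.2%; serious distortion needs about half the sample. Nothing here supports a claim that the pilot's result would be invalid. The reason to act is that the remedy completes a safeguard already chosen and costs almost nothing.

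**What to change.** First check whether the information sheet or consent form already carries a wider request. If not:

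1. After each encounter, remind participants not to discuss the scenario with anyone who is, or may become, a participant until the study closes. Exempt the study interview and any support service. A flat ban on telling anyone would clash with the interview questions about the scenarios (Appendix 9) and with the support offered after distress (section 3.7).
2. Before each encounter, once the task sheet has been read, ask one yes/no question: did you know anything about this case before today?
3. In section 7.2, state that the BAS comparison will be repeated without those who answer yes, as a descriptive sensitivity analysis.
4. In section 3.5, state how many scenario versions are used at each time point.

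Cost: a few sentences and one tick box per encounter, with no extra visit or staff. Limits: some participants may not admit prior knowledge, so a no is weak evidence, and dropping even a few of 15-20 participants leaves an imprecise estimate. Even so, the report could say that the question was asked and how many answered yes.
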